8. STUDY PROCEDURES

8.1 Schedule of study procedures

Before study entry, throughout the study, and following study drug discontinuation, various clinical and diagnostic laboratory evaluations are outlined. The purpose of obtaining these detailed measurements is to ensure adequate safety and tolerability assessments. Clinical evaluations and laboratory studies may be repeated more frequently if clinically indicated. The Schedules of Assessments during the screening and treatment period is provided following the Protocol Synopsis.

8.1.1 Screening Phase

Screening procedures will be performed up to 28 days prior to study registration, unless otherwise specified. All subjects must first read, understand, and sign the IRB/REB/IEC-approved ICF before any study-specific screening procedures are performed. After signing the ICF, completing all screening procedures, and being deemed eligible for entry, subjects will be enrolled in the study. Procedures that are performed prior to the signing of the ICF and are considered standard of care may be used as screening assessments if they fall within the 28-day screening window. An archived pre-treatment tumor biopsy obtained outside of the 28-day screening window may be used for PD-L1 staining if the subject has not received any interval treatment since undergoing the biopsy.

The following procedures will be performed during the Screening Visit:

- Informed Consent
- Review of eligibility criteria
- Medical history and demographics
- Adverse event/serious adverse event assessment with prior immunotherapy
- Complete physical exam
- ECOG Performance Status
- Vitals signs, weight and height

Drug Substance Azacitidine/Decitabine (ASTX727)

Study Code 15-11430

Edition Number 13.0

Date 09202024

- 12-lead ECG (in triplicate [2-5 minutes apart])
- Tumor biopsy
- Peripheral blood draw for research analysis
- Review of prior/concomitant medications
- Imaging by CT/MRI
- Bone scan
- Clinical laboratory tests for:
 - o Hematology (see Table 7)
 - o Clinical chemistry (see Table 8)
 - o TSH
 - o Coagulation (PT, PTT, INR)
 - o Creatinine Clearance
 - o Serum pregnancy test (for women of childbearing potential only)
 - o Hepatitis B and C serologies
 - HIV testing
 - o Urinalysis (see Table 9)

8.1.2 Treatment Phase

Procedures to be conducted during the treatment phase of the study are presented in the Schedule of Assessments. Screening procedures performed within 72 hours of Cycle 1 Day 1 (C1D1) of protocol treatment do not need to be repeated on C1D1. The treatment to be used in this trial is outlined below in **Table 6**.

- Complete physical exam
- Vitals signs and weight
- 12-lead ECG (in triplicate [2-5 minutes apart]), as clinically indicated
- ECOG Performance Status
- Adverse event/serious adverse event assessment
- Review of prior/concomitant medications
- Clinical laboratory tests for:
 - o Hematology (see Table 7)
 - o Clinical chemistry (see Table 8)
 - o TSH
 - o Coagulation (PT, PTT, INR), as clinically indicated
 - o Creatinine Clearance
 - o Serum pregnancy test (for women of childbearing potential only)
 - o Urinalysis (see Table 9)

Drug Substance Azacitidine/Decitabine (ASTX727)

Study Code 15-11430

Edition Number 13.0

Date 09202024

- Pharmacokinetic assessment
- Imaging by CT/MRI
- Bone scan, if baseline bone scan demonstrates metastatic disease
- Tumor biopsy sample for research analysis
- Peripheral blood draw for research analysis

Table 9 Trial Treatment

Drug	Dose/Potency	Dose Frequency	Route of Administration	Regimen/Treatment Period	Use
Durvalumab (MEDI4736)	1500 mg	Q4W	IV infusion	Day 1 of each 4 week cycle for 12 cycles ^a	Experimental
Tremelimumab	75 mg	Q4W	IV infusion	Day 1 of each 4 week cycle for 4 cycles ^a	Experimental
Tremelimumab	300 mg	Once	IV infusion	Day 1 of Cycle 2	Experimental
Azacitidine	40 mg/m2 or 75 mg/m2	QD	SC	Days 1-5 or Days 1-5 and 8-12 of each 4 week cycle for 12 cycles ^a	Experimental
Decitabine (ASTX727)	35 mg decitabine	QD	PO	Days 1-3, 1-4, or 1-5 of each 4-week cycle for 12 cycles ^a	Experimental

^aAzacitidine or decitabine will be administered alone in Cycle 1. For those patients receiving azacitidine, the combination of azacitidine, durvalumab, and tremelimumab therapy will start in Cycle 2. Patients will continue with azacitidine, durvalumab and tremelimumab combination therapy for Cycles 3-5 and azacitidine and durvalumab for Cycles 6-12. For those patients receiving decatibine, the combination of decatibine and durvalumab therapy will be given in Cycles 2-12.

8.1.3 End of Treatment

End of treatment is defined as the last planned dosing visit within the 12-month dosing period. For subjects who discontinue azacitidine or oral decitabine (ASTX727), durvalumab (MEDI4736), or tremelimumab prior to completing the 12 months of treatment with combination therapy, end of treatment is considered the last visit where the decision is made to discontinue treatment. All required procedures must be completed within \pm 28 days of the end of treatment visit. Repeat disease assessment is not required if performed within 28 days prior to the end of treatment visit.

Assessments for subjects who have completed azaciditine, or oral decitabine, durvalumab (MEDI4736), and tremelimumab treatment and achieved disease control, or have discontinued

Drug Substance Azacitidine/Decitabine (ASTX727)

Study Code 15-11430

Edition Number 13.0

Date 09202024

azaciditine, or decitabine, durvalumab (MEDI4736) or tremelimumab due to toxicity in the absence of confirmed progressive disease are provided in APPENDIX 2

Assessments for subjects who have discontinued azaciditine, or decitabine, durvalumab (MEDI4736), or tremelimumab treatment due to confirmed PD are presented in **Appendix 3**.

All subjects will be followed for survival until the end of the study regardless of further treatments, or until the sponsor ends the study.

8.2 Description of study procedures

8.2.1 Medical history and physical examination, electrocardiogram, weight and vital signs

Findings from medical history (obtained at screening) and physical examination shall be given a baseline grade according to the procedure for AEs. Increases in severity of pre-existing conditions during the study will be considered AEs, with resolution occurring when the grade returns to the pre-study grade or below.

Physical examinations will be performed on study days noted in the Schedule of Assessments.

8.2.2 Physical examination

Physical examinations will be performed according to the assessment schedule. Full physical examinations will include assessments of the head, eyes, ears, nose, and throat and the respiratory, cardiovascular, GI, urogenital, musculoskeletal, neurological, dermatological, hematologic/lymphatic, and endocrine systems. Height will be measured at Screening only. Targeted physical examinations are to be utilized by the Investigator on the basis of clinical observations and symptomatology. Situations in which physical examination results should be reported as AEs are described in Section 10

8.2.3 Electrocardiograms

Resting 12-lead ECGs will be recorded at screening and as clinically indicated throughout the study. ECGs should be obtained after the patient has been in a supine position for 5 minutes and recorded while the patient remains in that position.

In case of clinically significant ECG abnormalities, including a QTcF value >470 ms, 2 additional 12-lead ECGs should be obtained over a brief period (eg, 30 minutes) to confirm the finding.

Situations in which ECG results should be reported as AEs are described in Section 10.0.

8.2.4 Vital signs

Vital signs (blood pressure [BP], pulse, temperature, and respiration rate) will be evaluated according to the assessment schedules.

On infusion days, patients receiving durvalumab (MEDI4736) + tremelimumab treatment will be monitored during and after infusion of IP as presented in the bulleted list below.

Supine BP will be measured using a semi-automatic BP recording device with an appropriate cuff size, after the patient has rested for at least 5 minutes. BP and pulse will be collected from patients receiving durvalumab (MEDI4736) + tremelimumab treatment before, during, and after each infusion at the following times (based on a 60-minute infusion):

Prior to the beginning of the infusion (measured once from approximately 30 minutes before up to 0 minutes [ie, the beginning of the infusion]).

Approximately 30 minutes +/- 5 minutes during the infusion (halfway through infusion).

At the end of the infusion (approximately 60 minutes +/-5 minutes).

In the 1-hour observation period post-infusion: 30 and 60 minutes after the infusion (ie, 90 and 120 minutes from the start of infusion) (+/- 5 minutes) is required after the first infusion of durvalumab (MEDI4736) and tremelimumab and then for subsequent infusions as clinically indicated.

If no clinically significant infusion reactions are observed during or after the first cycle, subsequent infusion observation periods can be at the Investigator's discretion (suggested 30 minutes +/- 5 minutes after each durvalumab (MEDI4736) and tremelimumab infusion).

If the infusion takes longer than 60 minutes, then BP and pulse measurements should follow the principles as described above or be taken more frequently if clinically indicated. The date and time of collection and measurement will be recorded on the appropriate eCRF. Additional monitoring with assessment of vital signs is at the discretion of the Investigator per standard clinical practice or as clinically indicated.

Body weight is also recorded along with vital signs on the days of infusion of durvalumab +/-tremelimumab.

Situations in which vital signs results should be reported as AEs are described in Section 10.3. A complete physical examination will be performed and will include an assessment of the following (as clinically indicated): general appearance, respiratory, cardiovascular, abdomen,

Drug Substance Azacitidine/Decitabine (ASTX727)

Study Code 15-11430

Edition Number 13.0

Date 09202024

skin, head and neck (including ears, eyes, nose and throat), lymph nodes, thyroid, musculo-skeletal (including spine and extremities), genital/rectal, and neurological systems and at screening only, height.

8.2.5 Clinical laboratory tests

The following clinical laboratory tests will be performed (see the Schedule of Assessments)

- Coagulation parameters: Activated partial thromboplastin time and International normalised ratio to be assessed at baseline and as clinically indicated
- Pregnancy test (female subjects of childbearing potential only)
 - o Urine human chorionic gonadotropin
 - o Serum beta-human chorionic gonadotropin (at screening only)
- Thyroid Stimulating Hormone
 - o free T3 and free T4 only if TSH is abnormal

Table 10. Hematology Laboratory Tests

Basophils Mean corpuscular volume
Eosinophils Monocytes
Hematocrit Neutrophils
Hemoglobin Platelet count
Lymphocytes Red blood cell count
Mean corpuscular hemoglobin Total white cell count
Mean corpuscular hemoglobin concentration

Drug Substance Azacitidine/Decitabine (ASTX727)

Study Code 15-11430

Edition Number 13.0

Date 09202024

Table 11. Clinical chemistry (Serum or Plasma) Laboratory Tests

Albumin	Glucose
Alkaline phosphatase	Lactate dehydrogenase
Alanine aminotransferase	Lipase
Amylase	Magnesium
Aspartate aminotransferase	Potassium
Bicarbonate	Sodium
Calcium	Total bilirubin ^a
Chloride	Total protein
Creatinine	Urea or blood urea nitrogen, depending on local practice
Gamma glutamyltransferase ^b	Uric acid

^a If Total bilirubin is ≥2xULN (and no evidence of Gilbert's syndrome) then fractionate into direct and indirect bilirubin

Table 12. Urinalysis Tests^a

Bilirubin	pH
Blood	Protein
Glucose	Specific gravity
Ketones	Colour and appearance

^a Microscopy should be used as appropriate to investigate white blood cells and use the high power field for red blood cells

8.3 Biological sampling procedures

8.3.1 Biomarker sampling and evaluation methods

A tumor biopsy will be obtained pre- and either on- or post-treatment while on the study. A biopsy will be obtained on week 8 during the phase 1b dose-escalation portion of the study. The tumor samples will be evaluated for changes in LINE-1 methylation and/or expression of CD8+ T cells and MHC Class I/II by immunofluorscent staining and quantitative analysis. Other immune biomarkers which will be evaluated include, but are not limited to: PD-1, PD-L1, PD-L2, CD80, CD4, CD8, FoxP3, CTLA-4, Lag-3, Tim-3, IFN-g, and HPV-specific CD8+ T cells for HPV-associated tumors.

^b At screening, Cycle 1 Day1, and as clinically indicated

Clinical Study Protocol
Drug Substance Azacitidine/Decitabine (ASTX727)

Study Code 15-11430 Edition Number 13.0

Date 09202024

In addition, blood and stool samples for correlative biomarker studies will be collected at preand either on- or post-treatment. The blood will be evaluated for changes in circulating HPVspecific CD8+ T cells, for tumor DNA circulating markers, and cytokines. The stool will be used to characterize the microbiome in the gut and the microbiome correlated with response to immunotherapy.

PD-L1 Testing

To ensure comparability of data across all studies of durvalumab (MEDI4736) and/or tremelimumab and to gain real world experience on the performance of this assay, it is strongly encouraged that all studies that include PD-L1 testing utilize the Ventana SP263 assay. Testing should be restricted to the Ventana SP263 assay and should be performed in accordance with the package insert on the Ventana Benchmark platform (Ultra or XT).

The Ventana SP263 assay is fully analytically validated test characterized through to the completion of reader precision studies in the non-small cell lung cancer (NSCLC) and squamous cell carcinoma of the head & neck (SCCHN). For these tumors, the Ventana SP263 assay has a fully reproducibility data package supporting cut-off and scoring algorithm.

Sample collection for PD-L1 testing

- The preferred tumor sample for the determination of a patient's PD-L1 status is the one taken following the completion of the most recent prior line of therapy. Samples taken at this time reflect the current PD-L1 status of the tumor and considered clinically most relevant.
- The preferred sample for PD-L1 testing is less than or equal to 3 months old. In cases where a sample a less than 3 months old is not available, patients can be asked to undergo a new biopsy if considered clinically appropriate by their treating physician.
- Samples should be collected via a core needle of 18 gauge or larger or be collected by an incisional or excisional tumor biopsy. Where institutional practice uses a smaller gauge needle, samples should be evaluated for tumor cell quantity (i.e. >100 tumor cells) to allow for adequate PD-L1 immunohistochemistry analyses.
- When the collection of a new sample is not clinically appropriate, archival samples may be utilized provided the specimen it is not older than 3 years of age. When archival samples are used to assess PD-L1 status, the age of the sample / date of collection should be captured.

Study Code 15-11430

Edition Number 13.0

Date 09202024

• Samples submitted for PD-L1 testing should be formalin fixed and embedded in paraffin. Samples from fine needle aspirates (FNA) or decalcified bone are not appropriate for PD-L1 analysis.

8.3.2 Estimate of volume of blood to be collected

The total volume of blood that will be drawn from each subject in this study is as follows:

Table 13. Volume of blood to be drawn from each subject

Assessment		Sample volume (mL)	No. of samples	Total volume (mL)
Safety	Clinical chemistry	5	12	60
	Hematology	5	12	60
Biomarker		50	2	100
Total				220

8.3.3 Archival tumor samples and fresh tumor biopsies

8.3.3.1 Archival tumor samples

A pre-treatment tumor biopsy sample will be retrieved when available, either as a formalin-fixed paraffin-embedded (FFPE) tissue block or up to 20 unstained slides. The archival tumor biopsy sample will be shipped to and stored in the laboratory of [name] for analysis. Analyses which will be conducted include, but are not limited to, LINE-1 methylation status, PD-L1 expression, tumor mutation analysis, RNA analysis, and MHC Class I/II and CD8+ T cell immunohistochemistry. After the clinical study report has been finalized, the archival FFPE will be returned to the original hospital, if requested, and any unstained slides will be retained for future research.

8.3.3.2 Fresh tumor biopsies

A fresh tumor biopsy will be obtained in all subjects pre-treatment and either on- or post-treatment, if safely accessible for biopsy as determined by the treating physician. A biopsy will be obtained on week 8 during the phase 1b dose-escalation portion of the study. The fresh tumor biopsy sample will be shipped to and stored in the laboratory of [name] for analysis. Analyses which will be conducted include, but are not limited to, LINE-1 methylation, PD-L1 expression, tumor mutation analysis, RNA analysis, and MHC Class I, II and CD8+ T cell immunofluorescence. The pre-, on- or post-treatment biopsy can only be waived if the location

Date 09202024

of the lesion is not safely accessible for biopsy, as determined by the treating physician. The on-treatment biopsy will be performed at the time of confirmed PR on imaging, as outlined above. For the non-superficial lesions, the on-treatment core needle biopsy will be performed under image guidance, either CT, MRI, or ultrasound. For dermal lesions, a core needle, excisional, or punch biopsy can be performed without image guidance. Biopsies will be obtained of lesion(s) which have decreased in size. A biopsy of a progressing lesion can also be obtained at the same time based on the discretion of the physician performing the procedure and the Investigator. Any biopsied lesion(s) can no longer be included in the objective tumor response assessment except for those patients whom only have one target lesion which is greater than 2 cm in diameter in any one direction. A post-treatment biopsy will be obtained in those patients who stop study treatment prior to completing 12 months of therapy or any patients who completes 12 months of therapy but did not undergo an on-treatment biopsy. Patients who had an on-treatment biopsy may undergo a post-treatment biopsy at the time of completing 12 months of therapy; however, this is not a mandatory biopsy. Any patient who restarts treatment will require another biopsy prior to restarting treatment. The fresh tumor biopsy sample will be shipped to and stored in the laboratory of [name] for analysis. At a minimum, 3 core biopsies will be obtained and 1 core will be formalin fixed and the other 1-2 cores will be flash frozen. Analyses which will be conducted include, but are not limited to, LINE-1 methylation, PD-L1 expression, tumor mutation analysis, RNA analysis, and MHC Class I/II and CD8+ T cell immunohistochemistry. After the clinical study report has been finalized, any retaining tissue will be retained for future research.

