4.1 Inclusion criteria

For inclusion in the study, patients should fulfill the following criteria:

- 1. Written informed consent and any locally-required authorization (e.g., HIPAA in the USA, EU Data Privacy Directive in the EU) obtained from the subject prior to performing any protocol-related procedures, including screening evaluations
- 2. Age \geq 18 years at time of study entry or adult male or female (according to age of majority as defined as \geq 18 years)

²MTD (maximally tolerated dose)

²MTD (maximally tolerated dose)

³BED (biologically effective dose)

Drug Substance Azacitidine/Decitabine (ASTX727)

Study Code 15-11430

Edition Number 13.0

Date 09202024

- 3. Histologically confirmed recurrent or metastatic SCCHN (oral cavity, oropharynx, hypopharynx, larynx, or unknown primary) not amenable to therapy with curative intent (surgery or radiation therapy with or without chemotherapy). Patients who refuse radical resection are eligible.
- 4. Tumor progression or recurrence during or after treatment with anti-PD1, anti-PDL1, anti-PDL2, anti-CTLA4, and/or other combination of immunotherapy.
- 5. Must give valid written consent to provide archival FFPE and/or newly acquired tumor tissue for the purpose of establishing baseline PD-L1 status as well as consent to provide on- and/or post-treatment tumor biopsy sample.
- 6. Eastern Cooperative Oncology Group (ECOG) performance status of 0 or 1 at enrollment
- 7. Life expectancy of ≥ 6 months
- 8. At least 1 lesion that can be accurately measured at baseline as ≥ 10 mm in the longest diameter (except lymph nodes which must have a short axis ≥15 mm) with CT or MRI and that is suitable for accurate repeated measurements as per RECIST 1.1 guidelines.
- 9. Adequate normal organ and marrow function as defined below (within 28 days prior to study registration):
 - Hemoglobin $\ge 8.0 \text{ g/dL}$
 - Absolute neutrophil count (ANC) ≥ 1.0×10^9 /L (≥ 1500 per mm³)
 - Platelet count $\geq 100 \times 10^9 / L \ (>100,000 \text{ per mm}^3)$
 - Serum bilirubin ≤ 1.5 x institutional upper limit of normal (ULN). This will not apply to subjects with confirmed Gilbert's syndrome (persistent or recurrent hyperbilirubinemia that is predominantly unconjugated in the absence of hemolysis or hepatic pathology), who will be allowed only in consultation with their physician.
 - AST (SGOT)/ALT (SGPT) \leq 2.5 x institutional upper limit of normal unless liver metastases are present, in which case it must be \leq 5x ULN

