9. DISEASE EVALUATION AND METHODS

The response to immunotherapy may differ from the typical responses observed with cytotoxic chemotherapy including the following (Wolchok et al 2009, Nishino et al 2013):

- Response to immunotherapy may be delayed
- Response to immunotherapy may occur after PD by conventional criteria
- The appearance of new lesions may not represent PD with immunotherapy
- SD while on immunotherapy may be durable and represent clinical benefit.

Based on the above-described unique response to immunotherapy and based on guidelines from regulatory agencies, e.g., European Medicines Agency's "Guideline on the evaluation of anti-cancer medicinal products in man" (EMA/CHMP/205/95/Rev.4) for immune modulating anti-cancer compounds, the study may wish to implement the following in addition to standard RECIST 1.1 criteria:

- RECIST will be modified so that PD must be confirmed at the next scheduled visit, preferably, and no earlier than 4 weeks after the initial assessment of PD in the absence of clinically significant deterioration. Treatment with durvalumab (MEDI4736), tremelimumab, and azacitidine or oral decitabine (ASTX727) would continue between the initial assessment of progression and confirmation for progression.
- In addition, subjects may continue to receive durvalumab (MEDI4736), tremelimumab, and azacitidine or oral decitabine (ASTX727) beyond confirmed PD in the absence of clinically significant deterioration and if investigators consider that subjects continue to receive benefit from treatment.

Modification of RECIST as described may discourage the early discontinuation of durvalumab (MEDI4736), tremelimumab, and azacitidine or oral decitabine (ASTX727) and provide a more complete evaluation of its anti-tumor activity than would be seen with conventional response criteria. Nonetheless, the efficacy analysis will be conducted by programmatically deriving each efficacy endpoint based on RECIST 1.1 criteria.

Of note, clinically significant deterioration is considered to be a rapid tumor progression that necessitates treatment with anti-cancer therapy other than durvalumab (MEDI4736) + tremelimumab or with symptomatic progression that requires urgent medical intervention (e.g., central nervous system metastasis, respiratory failure due to tumor compression, spinal cord compression).

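### The biopsied-lesion rule conflicts with the measurable-disease criterion and leaves the RECIST tumor sum undefined once a target lesion is sampled

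*Combined protocol and SAP*

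**What the plan says.** Section 8.3.3.2 (Fresh tumor biopsies) sets the exclusion rule: "Any biopsied lesion(s) can no longer be included in the objective tumor response assessment except for those patients whom only have one target lesion". The exception carries a size condition, that the lesion be one "which is greater than 2 cm in diameter in any one direction". The section does not say whether that size is taken at baseline or at biopsy.

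On timing, the same section says "A biopsy will be obtained on week 8 during the phase 1b dose-escalation portion of the study" and later "The on-treatment biopsy will be performed at the time of confirmed PR on imaging, as outlined above". On the choice of lesion it says "Biopsies will be obtained of lesion(s) which have decreased in size"; a progressing lesion may be sampled as well, at the physician's discretion. The biopsy can be waived only when the location "of the lesion is not safely accessible for biopsy, as determined by the treating physician".

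Inclusion criterion 8 (Section 4.1) requires "At least 1 lesion that can be accurately measured at baseline as ≥ 10 mm in the longest diameter", with lymph nodes entering at a short axis of 15 mm or more. Section 9 says "the efficacy analysis will be conducted by programmatically deriving each efficacy endpoint based on RECIST 1.1 criteria". Section 9.1.1 requires a response to be confirmed at the next scheduled scan, at least 4 weeks later, with scans every 8 weeks.

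No section says what happens to the baseline or nadir sum when a target leaves the assessment, or how a patient with no remaining target is classified.

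**The concern.** Two size limits in the same protocol do not meet. A patient can satisfy the measurable-disease criterion with one small lesion, have it sampled as the protocol requires, and then have no target lesion for the response assessment.

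In patients with several targets, RECIST change is a ratio of sums. If a target leaves partway through, someone must decide whether it also leaves the denominator. The plan derives the endpoints by program but gives the programmer no instruction, and the choice can decide the response category.

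There is also a conditional problem. If the lesion is picked because it shrank, and is taken at week 8 before the response has been confirmed, then lesions are removed on the basis of the outcome being measured.

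At stake are the response rate and PFS, which Figure 1 lists as outcomes, and the RECIST-based PFS in the research hypothesis (Section 1.2). Sections 3.1 and 5.1.3 also tie continuation and retreatment to confirmed response and later progression in target lesions, so the classification is used during the trial as well as in the report.

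**Working it through.** The plan gives no figure of its own on this point. The check compares the stated limits and then works examples with assumed lesion sizes.

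**1. Eligibility against the exception.**
- Eligible: sole lesion of 10 mm or more (Section 4.1).
- Kept after biopsy: sole target above 20 mm (Section 8.3.3.2).
- Gap: a sole target from 10 to 20 mm is eligible but not kept. For a node, the gap is a short axis from 15 to 20 mm with no dimension above 20 mm, because the exception accepts any direction.
- Waiver: unsafe access only; none for a small or sole lesion. The schedule's footnote p lets archival tissue serve at baseline, but nothing replaces the week-8 sample. Section 11 counts a patient as evaluable for BED only with that sample.
- Undefined case: a sole 25 mm target that shrinks by 30% measures 25 × 0.70 = 17.5 mm. It is above the limit at baseline and below it at biopsy.

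**2. Tumor sum with several targets.** Percent change = (follow-up sum / baseline sum) − 1. Lesion A is the sampled one; sizes in mm are assumptions.

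| Assumed sizes | Both kept | A out of baseline and follow-up | A out of follow-up only |
|---|---|---|---|
| A 40 to 20, B 30 to 28 | 48/70 − 1 = −31.4% | 28/30 − 1 = −6.7% | 28/70 − 1 = −60.0% |
| A 30 to 20, B 30 to 36 | 56/60 − 1 = −6.7% | 36/30 − 1 = +20.0% | 36/60 − 1 = −40.0% |

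The protocol cites RECIST 1.1 without printing its limits. I assume the usual ones: a fall of at least 30% for PR, and a rise of at least 20% and 5 mm over the smallest sum for PD, with baseline as the smallest sum here. The first patient is then PR, SD or PR by convention. The second is SD, PD (a rise of 6 mm, exactly at the 20% limit) or PR.

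**3. Timing.** The first scheduled scan and the dose-escalation biopsy both fall at week 8, and the text does not fix their order. Confirmation of a week-8 response falls at the next scan, week 16. A target sampled at week 8 therefore cannot help confirm the response it showed. If the biopsy is instead done at confirmed PR, the response already stands and only later assessments (duration, progression) can change.

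**4. Leverage.** Section 11 expects about 28 evaluable patients on oral decitabine. If that were the response denominator (the section defines none), one reclassified patient would move the response rate by 1/28 = 3.6 percentage points.

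**The case against.** The strongest reply is that response is not an objective. The primary objective is the BED and the secondary is safety; Section 11 has no response or PFS analysis; escalation, stopping and expansion rest on LINE-1 methylation, immune markers and toxicity. This stands, and it caps the importance of the point. A reader might infer that the dose decision is compromised; the documents do not support that.

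Second, the instruction to sample shrinking lesions follows directly after the sentence on confirmed PR and may apply only to that biopsy. The week-8 biopsy carries no such criterion of its own. A reader might infer that the rule systematically turns responders into non-responders. That does not follow: the timing text is in conflict, a progressing lesion may also be sampled, and the two baseline conventions push the result in opposite directions.

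Third, removing a lesion from the assessment most naturally means removing it from both sums, so the −60.0% result needs a less natural reading. That is fair, but the text does not settle it, and the natural reading still moves the first example from PR to SD.

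Fourth, a reader might infer that the small-lesion patient has nothing left to assess. At most there is no target lesion: non-target and new lesions and survival are still followed, and the sampled lesion need not be the target if other disease is suitable. Many nodes would also meet the exception through their long axis.

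Fifth, excluding sampled lesions is a defensible way to avoid measurements altered by the procedure, which takes at least 3 cores. Keeping every core-sampled target is therefore debatable, most of all for a small one.

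**Conclusion.** The point holds as an internal conflict and a missing rule. Following the text as written, an eligible patient with a sole target of 10 to 20 mm has no target lesion once it is sampled. In patients with several targets, the response category after a biopsy can depend on a convention the plan does not state: −31.4%, −6.7% or −60.0% for the same assumed patient.

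Selection on the outcome is conditional. It arises if the lesion is chosen because it shrank and is taken at week 8, before confirmation.

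The effect is confined to response rate, PFS and response-based status. The number of patients affected cannot be computed, because the documents give no distribution of lesion sizes or counts, and the direction of bias is not fixed. The categories in the examples rest on assumed sizes and the usual RECIST limits. The point should be corrected, but it does not undermine the primary analysis.

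**What to change.** 1. Align the sole-target exception with inclusion criterion 8, so that a sole target stays in the assessment whatever its size and is flagged as sampled. This also removes the question of when the 2 cm is measured.
2. Prefer a suitable non-target lesion for biopsy, and do the week-8 scan before the week-8 biopsy.
3. When a target is excluded, recompute the baseline and nadir sums without it from that point on. Keep measuring it, and report a sensitivity analysis that leaves core- or punch-sampled targets in the sum.
4. Reconcile the week-8 and confirmed-PR biopsy passages in Section 8.3.3.2, and state to which biopsy the instruction to sample shrinking lesions applies.

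The cost is protocol wording, one extra field on the response form and a short programming rule; no scan or biopsy is added. The downside is some measurement noise from sampled lesions that stay in the sum, which the flag and the sensitivity analysis make visible.
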